2.0 Approach

Study Aims: Our *long-term goal* is to increase uptake of CRC screening by informing and improving patient and provider discussion and decisions. The *main objective* of this study is to test whether providing patients and their providers with personalized messages about ACN risk results in higher screening uptake and higher decision quality (i.e., informed choice and receipt of the preferred screening test), compared to an approach that does not utilize ACN risk.

Aim 1: To measure the impact on patient decision quality and screening uptake of providing patients and their providers with personalized messages about the patient’s current risk of having advanced colorectal neoplasia (ACN).

Aim 2: To examine mediators and moderators of the interventions' effectiveness.

To achieve Aim 1, we will test the following hypotheses:

Primary hypotheses:

1. The proportion of patients who make a **high-quality decision** and **complete screening** at six months will be higher:

- 1.1 for patients who receive the personalized message than for those who do not, and
- 1.2 for patients whose providers receive the personalized message than for those whose providers do not.

Secondary hypotheses:

2. Among patients with low risk of ACN, the proportion who make a **high-quality decision** and **undergo a stool blood test (FIT)** by six months will be higher

- 2.1 for patients who receive the personalized message than for those who do not, and
- 2.2 for patients whose providers receive the personalized message than for those whose providers do not.

3. Among patients with high-average risk of ACN, the proportion who make a **high-quality decision** and **undergo a colonoscopy** by six months will be higher

- 3.1 for patients who receive the personalized message than for those who do not, and
- for patients whose providers receive the personalized message than for those whose providers do not.

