3.1 Primary Outcome Measures

The primary outcomes are screening uptake and decision quality, each of which is essential to providing high-quality and patient-centered care.

- Screening uptake will be defined as performance of colonoscopy, FIT, or another approved screening test within six months after enrollment, as documented in the EHR.
- Decision quality will be defined by the multi-dimensional measure of informed consent (MMIC),⁵³ where a high-quality decision is one where the individual has adequate knowledge regarding the available options and undergoes the intervention that he or she has chosen or that fits his or her values (“value concordance”). (PC-3, IR-4)
 - Knowledge (T2) will be assessed by a 12-item test made up of 6 multiple choice questions and 6 true-false questions that was updated from what we used in our previous study to reflect changes in screening guidelines. Adequate knowledge = 9 correct
 - Concordance (T3) will be measure between the test choice at T2 and screening test underwent, if any, within six months after enrollment(T3).

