10.0 Statistical Considerations

Sample Size Justification: This trial is powered for the two primary hypotheses. For Aim 1, we expect exposure to either personalized message will increase uptake from 30%, which was the uptake at six months seen in our current PCORI project, to 40% and the combined effect to be additive (i.e. no interaction between the interventions). We believe a 10% increase in uptake is a minimally important difference to detect. An earlier study found that patients who viewed a personalized message about risk of colorectal cancer had a 9% higher uptake than did those who viewed a non-personalized message (CI-2).⁴¹ We believe our intervention will have greater impact, due to its encouraging low-risk individuals (50% of patients)⁷ to use a non-invasive test. An earlier study found that individuals due for screening who were offered a non-invasive test had a 31% higher rate of screening than those offered just colonoscopy (69% vs. 38%)(CI-2).⁵ To detect an effect of 10% increase (odds ratio of 1.55) with a power

of 80% (two-sided $\alpha=0.05$) a sample size of 732 subjects (183 per group) is needed for the Wald test for either patient or provider message main effect in a logistic model if patient outcomes were independent. To account for clustering due to randomization by provider, we inflate the sample size based on the design effect. We assume an intraclass correlation of .05 for provider, and average number of subjects per provider of 8. (RC-3) We will allow for an attrition rate of 10%. This results in a final sample size of 1100 (275 per group). For the informed choice outcome, we expect exposure to either personalized message would increase informed choice from 20%, the outcome in our current PCORI project, to 30% (odds ratio of 1.71) and the effect to again be additive. This leads to an initial sample size of 604 total (151 per group) before accounting for inflation and attrition, which is less than for uptake. Thus, the sample size needed for both outcomes is 1100 (275 per group, 130 providers). These recruitment goals are readily achievable based on the INFORM study. Aim 2 is considered exploratory because we don't have sufficient preliminary data to estimate all effect sizes; however, we will have sufficient power for some hypotheses. (IR-1)

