Analytic plan: Preliminary analyses will compare baseline demographic information across the four groups using means and standard deviations for continuous variables and frequency distributions for categorical variables. We will adjust for those characteristics in subsequent analyses if significant differences emerge at a conservative level for inclusion of a covariate ($p<.20$). Characteristics of participants who don't complete T1 and/or T2 will be compared with those who remain to determine what biases may exist. The above analyses will be conducted using ANOVA, chi-square tests, or exact or non-parametric equivalents. If there appear to be biases in dropout, we will conduct pattern mixture models analyses to see how the results could change based on the missing data assumption (IR-5, MD-2, MD-3, MD-4). Primary analysis of outcomes will employ an intent-to-treat analysis. For Aim 1, our primary hypotheses will be tested using logistic regression models with the outcomes of informed choice and uptake (both yes/no outcomes) and main effects for: 1) patient receipt of personalized message; and 2) provider receipt of personalized message. A random effect for provider will be included to account for the clustered randomization. We will test for an interaction effect, but do not expect one so have not powered the study for an interactive effect. The secondary hypotheses (planned subgroup analyses with low risk group) will be tested using the same model type (HT-2, HT-3). The secondary hypotheses are considered exploratory. For Aim 2, mediation effects (RQ-6) will be estimated in a logistic regression setting, fitting the appropriate mediation models using MPlus⁷⁶ and then testing indirect effects using the percentile bootstrap approach to estimate the indirect effect.⁷⁷ For primary analyses, we will fit models that estimate the effects of either or both of the interventions relative to control. Moderators (RQ-4, HT-1, HT-2, HT-3, HT-4) will be identified by significant interaction terms in the regression models from Aim 1.

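### The plan names two primary outcomes per message but no success rule, so either the 5% error rate or, for the provider message, the 80% power is not what is stated

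*Combined protocol and SAP*

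**What the plan says.** - **Outcomes.** Section 3.1 (and 3.0): "The primary outcomes are screening uptake and decision quality, each of which is essential to providing high-quality and patient-centered care".
- **Hypotheses.** Section 2.0 (and Specific Aims): "The proportion of patients who make a high-quality decision and complete screening at six months will be higher", first for the patient message (1.1), then for the provider message (1.2).
- **Analysis.** Section 10.0, Analytic plan: "our primary hypotheses will be tested using logistic regression models with the outcomes of informed choice and uptake (both yes/no outcomes"), each model having "main effects for: 1) patient receipt of personalized message; and 2) provider receipt of personalized message". That is two outcomes by two messages, four primary tests.
- **Sample size.** Section 10.0, Sample Size Justification, sizes uptake and informed choice one at a time and takes the larger result: "Thus, the sample size needed for both outcomes is 1100". Two-sided 0.05 appears here only; the analytic plan gives no significance level.
- **Not stated.** There is no rule for what counts as success when the outcomes disagree, no testing order, no alpha split and no other multiplicity method. The exploratory label is given only to the secondary hypotheses and Aim 2.

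**The concern.** Hypotheses 1.1 and 1.2 are the confirmatory claims. Suppose a message raises informed choice significantly but not uptake. The text allows that to be reported as a supported hypothesis, because a primary outcome was positive, or as an unsupported one, because the hypothesis says *and*. Whoever chooses after seeing the results also chooses the error rate. Each reading has its own cost: accepting either outcome at 0.05 raises the false-positive rate, and requiring both means that power computed for one outcome is not power for the hypothesis.

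**Working it through.** **Inputs from section 10.0.** Uptake 30% to 40% (odds ratio 1.55); informed choice 20% to 30% (odds ratio 1.71); effects additive; two-sided 0.05; 80% power; intraclass correlation 0.05; 8 patients per provider; attrition 10%; N = 1100. **From section 6.0:** the patient message is assigned to individuals when they enter Qualtrics; the other message is randomized by provider. **Assumed:** the correlation r between the two test statistics, which the plan does not give, is taken as 0 to 0.76. The top value is the correlation if every informed choice were also an uptake: (0.20 − 0.30×0.20)/√(0.30×0.70×0.20×0.80) = 0.14/0.183 = 0.76.

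**1. The plan's figures reproduce.** N = 2(1.960+0.842)²[1/(p0q0)+1/(p1q1)]/(ln OR)², with p1 taken from the rounded odds ratio.
- Uptake: p1 = 0.399, N = 730.0, or 732 in four equal groups.
- Informed choice: p1 = 0.299, N = 600.8, or 604.
- Design effect 1+(8−1)×0.05 = 1.35. Then 732×1.35/0.90 = 1098, rounded to 1100. Informed choice alone needs 604×1.35/0.90 = 906.

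**2. Power for one outcome, provider message.** Effective N = 1100×0.90/1.35 = 733.
- Uptake: Φ(2.802√(733/732) − 1.960) = 80.1%.
- Informed choice: Φ(2.802√(733/604) − 1.960) = 87.0%.

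**3. False-positive rate per message, no effect on either outcome.**

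| r | Either suffices | Both required |
|---|---|---|
| 0 | 1 − 0.95² = 9.75% | 0.25% |
| 0.3 | 9.5% | 0.5% |
| 0.5 | 9.1% | 0.9% |
| 0.76 | 8.0% | 2.0% |

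The last column is 2×5% minus the middle one. If a message truly affects only one outcome, the both-required rule errs at most 5% of the time.

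**4. Power when both are required, provider message** (bivariate normal, effective N 733). Three bases for the event rates:
- A: scaled from the plan's 732 and 604.
- B: difference in proportions at 30/40% and 20/30%, mean/SE = 0.10/√[(p0q0+p1q1)/(733/2)] = 2.85 and 3.15.
- C: log odds ratio at rates averaged over the other message, which under additivity are 35/45% and 25/35%; ln OR/SE = 2.76 and 2.94.

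| Basis | Uptake alone | Informed choice alone | Both, r = 0 | Both, r = 0.76 |
|---|---|---|---|---|
| A | 80.1% | 87.0% | 69.7% | 76.2% |
| B | 81.4% | 88.3% | 71.9% | 77.9% |
| C | 78.8% | 83.7% | 66.0% | 73.6% |

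**5. Same, patient message.** With a design effect near 1 (assumption), effective N = 1100×0.90 = 990. Both-required power is 85.6–88.4% on basis A and 82.9–86.5% on C, so about 83–89%; basis B adds about a point at the top.

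**6. Hochberg within a message, provider message, r = 0 to 0.76.** Uptake: A 78.4–78.9%, B 79.9–80.4%, C 76.7–77.3%. Informed choice: A 83.9–85.6%, B 85.4–87.1%, C 80.6–82.1%. Error per message is 4.4–5.0% (simulated).

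**The case against.** The best defence is that the plan already implies a rule. The hypotheses say *and*, and section 3.1 calls each outcome essential, so both must succeed and error is held at 5%. That stands as far as it goes: a reader might infer from the two separate tests that a message with no effect has nearly double the stated chance of a positive result, but this is true only if one outcome suffices, and no section says so. The defence does not rescue the plan, however, because under that rule the stated 80% is not the power of hypothesis 1.2. Nor is a composite available as an answer: *and* could describe one patient-level outcome, which would remove the two-outcome multiplicity, but none is defined, analysed or given a rate.

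Three other strong readings should be resisted.
- *Both hypotheses lose power.* Section 6.0 randomizes the patient message individually, so a both-required rule can keep at least 80% there.
- *The error rate is 15–18% over four tests.* That treats the two messages as one family. Section 5.0 adopts the 2x2 design to evaluate them separately, so the per-message figure is the fair one.
- *Nesting of informed choice in uptake can be relied on to soften the problem.* Section 3.2 makes no screening a test choice, and section 3.1 compares the choice with the test undergone, if any. An informed patient who declines and stays unscreened could therefore count as concordant, so 0.76 is only one end of an assumed range.

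**Conclusion.** The concern holds as an undefined success rule with a calculable consequence. Either-suffices gives about 8–10% error per message. Both-required gives error at or below 5%, with provider-message power of about 66–78% and patient-message power of about 83–89%. A composite has no stated power at all. These figures rest on the plan's own rates, intraclass correlation and attrition; an assumed correlation of 0 to 0.76; 0.05 being the level intended for the tests; and, for the patient message, a design effect near 1. The documents do not support saying that error is inflated as a matter of fact, that hypothesis 1.1 is underpowered, or that more patients are required.

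**What to change.** In section 10.0, Analytic plan, state one rule for each message, treat the two messages as separate factorial questions each at two-sided 0.05, and choose before outcome data are seen:

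- **(a) Outcomes claimed separately.** *Within each message the two primary outcomes are tested by the Hochberg procedure at two-sided 0.05: if both p-values are below 0.05 both are claimed; otherwise an outcome is claimed only if its p-value is below 0.025.* Hypotheses 1.1 and 1.2 in Specific Aims and section 2.0 must then be reworded as two outcomes, since the present *and* would contradict a claim on one alone.
- **(b) Both required.** *A message's hypothesis is supported only if uptake and informed choice are both significant at two-sided 0.05.* The hypotheses then need only say that two separate outcomes are meant.

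Make section 3.1 agree with the choice. In the Sample Size Justification restate power under it, separately for the provider and patient messages, with the assumed correlation. If a composite is intended instead, it needs its own definition, control rate and power.

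Cost: wording only, with N at 1100. Under (a) provider-message power is about 77–80% for uptake and 81–87% for informed choice, about 1 to 3 points below the unadjusted values. Under (b) the stated provider-message power falls below 80%.

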3.0 Outcome Measures/Endpoints

Choice of Outcomes (PC-3, RQ-6): The primary outcomes are screening uptake and decision quality, each of which is essential to providing high-quality and patient-centered care.

- Screening uptake will be defined as performance of colonoscopy, FIT, or another approved screening test within six months after enrollment, as documented in the EHR, as in our previous study.⁵¹
- Decision quality will be defined by the multi-dimensional measure of informed consent (MMIC),⁵³ where a high-quality decision is one where the individual has adequate knowledge regarding the available options and undergoes the intervention that he or she has chosen or that fits his or her values ("value concordance") (PC-3)(RQ-6). Sepucha et al. (2018) recently used the MMIC approach in the Colorectal Cancer Screening Decision Quality Instrument (CRC-DQI).⁵⁴ We will identify knowledge and the patient's intention to be screened shortly after a provider visit (T2). We will measure concordance between the test choice at T2 and screening test underwent, if any, within six months after enrollment (T3).⁵⁵⁻⁵⁸

Increasing screening uptake is an essential outcome since screening saves lives (RQ-6). Providers and healthcare institutions aim to get their patients screened, heeding the ethical principle of beneficence.⁵⁹ Our partner healthcare institutions have repeatedly expressed their desire to increase their screening rates(RQ-6). We heard the same message – the importance of getting patients screened – from lay people participating in our public deliberation exercise (RQ-6).⁶⁰ Both patients and lay people have emphasized, from the beginning of our work on CRC screening, and in the public deliberation, the importance of improving decision quality about CRC screening.(RQ-6) Patients who view decision aids as part of our studies often learn about FIT for the first time, and often respond that there should be more public awareness of this option.(RQ-6)

We chose not to make decision conflict⁶¹ or shared decision-making distal outcomes, due to our focus on screening uptake and quality of decision making. However, we will collect these subjective measures as potential mediators for the primary outcomes. Improved outcomes may result from patients feeling

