3.2 Secondary Outcome Measures

Patients: Data will be collected from patients at four time points: before they view the decision aid (T0); immediately after they view the decision aid (T1); aiming for 4-7 days after their appointment with their provider (T2); and six months after enrollment (T3).

- *Screening Intent* (T0, T1, T2): Intent to be screened for CRC with any test (“Screening Intent”), will be measured with 1 item: “Do you plan to get any type of colon test within the next 6 months?” and has a response option of: 5=Definitely, 4=Probably, 3=May or May not, 2=Probably not, and 1=Definitely not. This measure has been used in previous studies by our research team (PC-3, IR-4).^{51,52}
- *Test choice* (T0, T1, T2) (PC-3, IR-4): As in our previous studies:^{51,52}
 - For those who answer *Screening Intent* with “Definitely not,” “Probably not,” or “May or may not,” *Test Choice* is categorized as No screening.
 - Those who answer *Screening Intent* with “Probably” or “Definitely” have *Test Choice* categorized based on their answer to a single item: “If you have a colon test, which one would you choose?” Response options are: Stool test (FIT or Cologuard), Colonoscopy, Another test, or Don’t know.
- *Perceived CRC risk* (T0, T1, T2):
 - *Perceived personal CRC risk* will be assessed with a three-item scale, modified from items originally developed by Champion to measure perceived breast cancer risk^{78,79} and used by members of our team in multiple projects.^{51,52,69} Each item uses a four-point response option, where 1 = very unlikely and 4 = very likely, to assess participants’ beliefs about how likely they are to get CRC in the next 5 years, in the next 10 years and sometime during their lifetime. Cronbach alpha was 0.90 in our recent study. (PC-3, IR-4)
 - *Perceived comparative CRC risk* will be assessed with a single item measuring perceived comparative risk,⁶⁶ which asks “Compared to other women/men your same age, would you say your chance of getting colon cancer in the next 10 years is higher, about the same, lower, or don’t know?” (PC-3, IR-4)
- *Decision Conflict* (T0, T1, T2) will be assessed with the low literacy version of the Decision Conflict Scale, a ten-item instrument that assesses patients’ subjective feeling regarding the decision process over five areas and has been used widely in studies of decision aids (PC-3, IR-4).^{61,70}

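### Exploratory Aim 2 mediation test: baseline (T0) adjustment is not specified, and the plan's only covariate rule cannot control confounding between mediator and outcome

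*Combined protocol and SAP*

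**What the plan says.** Section 10.0 (Analytic plan) gives mediation one sentence: "mediation effects (RQ-6) will be estimated in a logistic regression setting, fitting the appropriate mediation models using MPlus", followed by "then testing indirect effects using the percentile bootstrap approach to estimate the indirect effect". No covariates are listed for the mediator or outcome equation. No assumption about confounding is stated, and no sensitivity analysis is planned for it.

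The only covariate rule is in the same paragraph. It starts from "Preliminary analyses will compare baseline demographic information across the four groups" and continues: "We will adjust for those characteristics in subsequent analyses if significant differences emerge at a conservative level for inclusion of a covariate", with the threshold set at p<.20.

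Section 3.0 names decision conflict and shared decision making as the subjective measures of interest: "we will collect these subjective measures as potential mediators for the primary outcomes". Its theoretical framework also expects the messages to change perceived susceptibility, benefits and barriers.

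Section 3.2 shows what is available at baseline. Decision conflict "will be assessed with the low literacy version of the Decision Conflict Scale, a ten-item instrument" at T0, T1 and T2. Screening intent ("Intent to be screened for CRC with any test") and perceived CRC risk are measured at the same three times. Shared decision making is measured at T2 only.

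Section 10.0 (Sample Size Justification) calls Aim 2 exploratory.

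**The concern.** The indirect effect is the product of two paths: message to mediator (a) and mediator to outcome (b). Randomisation protects a. It does not protect b, which is an observational association between a patient's later score and whether that patient is screened. A patient who starts with low conflict or high intent may well stay that way and also get screened. Then b is non-zero even if changing the mediator would change nothing.

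The p<.20 rule does not address this, for two reasons. It covers demographics, so T0 intent, T0 decision conflict and T0 perceived risk never come up for consideration. It also looks for association with arm, whereas confounding of b comes from association with both mediator and outcome. Extending the same screen to every T0 variable would still miss a well-balanced confounder.

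At stake is the mechanism that Aim 2 credits. A false indirect effect could steer later versions of the decision aid or provider message toward a target that does not drive screening.

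**Working it through.** **The plan's own figure.** Section 10.0 starts from 732 patients, an ICC of 0.05, 8 patients per provider and 10% attrition. 732 × (1 + 7 × 0.05) = 988.2, and 988.2 / 0.9 = 1098, stated as 1100. A Wald calculation for one main effect (30% base rate, OR 1.55) gives 730 against the stated 732. So the Aim 1 size reproduces. No error rate, power or effect size is given for Aim 2. The analysed number used below is 1100 × 0.9 = 990.

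**Model with no true mediation.** X is the patient message (1:1) and M0 is the T0 value in SD units. M = a·X + r·M0 + noise, with unit SD given X. Logit P(uptake) = −0.85 + 0.4·X + log(OR)·M0, with no term in M. The intercept gives 29.9% control uptake (plan: 30%), and 38.9% with the message (plan: 40%). Assumed, because the documents give no values: r = 0.4-0.6, OR = 1.25-1.5 per SD of M0, a = 0-0.5 SD.

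**Hand check.** If M0 is omitted, the spurious path is b ≈ r × log(OR).
- r = 0.4, OR 1.25: 0.4 × 0.223 = 0.089, a mediator odds ratio of 1.09 per SD.
- r = 0.6, OR 1.5: 0.6 × 0.405 = 0.243, an odds ratio of about 1.27.
- SE(b) ≈ 1/√(990 × 0.344 × 0.656) = 0.067, so z = 1.33 and 3.64. A 5% test of b alone rejects about 27% and 95%.
- SE(a) ≈ 2/√990 = 0.064. At a = 0.1 SD, z = 1.57 and power is 35%; at 0.2 SD, z = 3.15 and power is 88%; at 0, it is 5%.
- Multiplying the two rejection rates approximates the test of the product. At a = 0.2 SD: 0.88 × 0.27 = 24% up to 0.88 × 0.95 = 84%. At a = 0.1 SD: 9% up to 33%. At a = 0: at most 5%.

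**Simulation of the same model** (95% intervals for a·b by Monte Carlo draws; 600 runs per cell for shifts up to 0.1 SD, 1000 above). Rejection without T0 adjustment:

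| Message effect on mediator | OR 1.25 per SD | OR 1.5 per SD |
|---|---|---|
| 0 | 0-5% | 0-5% |
| 0.05 SD | 2-6% | 7-10% |
| 0.1 SD | 5-18% | 19-33% |
| 0.2-0.5 SD | 22-51% | 59-94% |

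A repeat of the last row gave 21-49% and 55-95%. If M0 is unrelated to uptake (OR 1.0), rejection at 0.2-0.5 SD is 4-6%. With M0 in both equations and measured without error, it is 4-6% (3-8% in the repeat). An actual percentile bootstrap at a = 0.3, r = 0.6, OR 1.5 (200 runs) rejected 96.5% unadjusted and 7.0% adjusted.

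**With clustering.** A second simulation used 984 patients (123 providers of 8), ICC 0.05, both messages at OR 1.55 and a provider-level percentile bootstrap. At a = 0.2 SD and r = 0.5 it rejected 49% (OR 1.35) and 83% (OR 1.65) unadjusted, against 7% adjusted in both. The indirect effect tested was that of the patient message; that of the provider message was not simulated.

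**Imperfect T0 measurement.** With T0 reliability 0.7 and r = 0.6, the residual path is b ≈ log(OR) × 0.6 × 0.3 / (1 − 0.36 × 0.7). For OR 1.5 this is 0.405 × 0.18 / 0.748 = 0.098. SE(b) becomes 0.067/√0.748 = 0.077, so z = 1.26 and rejection is about 24%. For OR 1.25, z = 0.69 and rejection is about 11%. Simulation at a = 0.3 SD gave 23.7% and 11.5%. Over shifts of 0.2-0.5 SD the range was about 10-27%.

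**The case against.** A reader might infer that the plan commits to an unadjusted test. It does not. It promises appropriate models, and a rule on when to add demographics does not exclude other terms. The T0 measures are collected and nothing bars their use. What stands is narrower: adjustment is unspecified, and the one stated rule would not supply it.

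A reader might also infer that any message effect on the mediator yields a false finding. The figures do not show that. Inflation is absent at zero shift and small at 0.05 SD. At 0.1 SD it is also absent if the T0 value predicts uptake only weakly (2-4% rejection at OR 1.1). The documents do not establish a shift of 0.2 SD or more. Both arms view a full decision aid. The falls in decision conflict reported in section 7.1 are before-and-after changes, not differences between message arms. Section 1.0 describes a trial of disclosing ACN risk with no significant impact on any measured outcome, though it argues that that trial's risk contrast was too small. Section 3.0 expects a shift but gives no size.

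Third, T0 adjustment might be taken as a cure. It restores the nominal level only when the T0 score captures the whole shared cause without error. Shared decision making, one of the two mediators named in section 3.0, has no T0 value. Perceived risk is a plausible mediator under the theoretical framework but is not named as one in the text.

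Finally, Aim 2 is exploratory. That lowers the weight of the point but does not make a confounded test informative. The same section still describes a formal test of indirect effects and expects enough power for some Aim 2 hypotheses.

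**Conclusion.** The concern holds as a gap in specification with a measurable consequence. If the mediation models are fitted under the p<.20 demographic rule alone, the test can reject 'no mediation' well above 5% when the mediator has no effect. This requires a baseline cause shared by mediator and outcome, and a message that moves the mediator. Under the assumed correlation (0.4-0.6) and odds ratio (1.25-1.5 per SD), rejection is about 0-5% with no shift, 5-35% at 0.1 SD and 20-95% at 0.2-0.5 SD. These inputs are assumptions and the range is wide. The documents do not show that the error will occur, and the Aim 1 tests are not affected. T0 adjustment removes most of the excess but can leave about 10-27% rejection if T0 reliability is 0.7 (correlation 0.6, shifts 0.2-0.5 SD). The change is worth making because the baseline values are already collected.

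**What to change.** In section 10.0, Aim 2, state that:
- every mediation model includes T0 screening intent in both the mediator and the outcome equation, whatever the p<.20 screen shows;
- where the mediator is measured at T0 (decision conflict, and perceived risk if it is used as a mediator), its T0 value also enters both equations;
- for shared decision making, measured at T2 only, both equations adjust for T0 intent, T0 decision conflict and T0 perceived risk;
- all indirect effects are reported as associational, with a sensitivity analysis for residual confounding between mediator and outcome.

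The cost is a few sentences of plan text, a few more model terms, one added sensitivity analysis, and the loss of a few patients who skipped T0 items. No new patients, visits or questionnaire items are needed.
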